Sample Size Considerations. As described in the original application (i.e., R01HD091155-A1), we conducted a conventional power analysis using G*Power (Version 3.1.9.5) and estimated the appropriate sample size for detecting differences in follow-up SDMT scores, controlling for baseline score (Specific Aim 1). Using G*Power, this was accomplished using the 'F test' selection within the 'Test' family menu, and the Statistical Test of 'ANCOVA: Fixed effects, main effects and interactions'. The effect size ($\eta_p^2=0.11$) for the power analysis was computed from our pilot RCT¹² of TMWX training compared with a waitlist control condition on SDMT scores in persons with MS who had mild ambulatory disability, but not CPS impairment. That effect size was smaller than the effect sizes for thalamocortical RSFC outcomes, and thus was included in the main power analysis as a conservative approach. The power analysis included standard assumptions of alpha (0.05) and beta (0.80). The power analysis indicated that the minimal total sample size for testing group differences on follow-up SDMT scores, controlling for baseline scores should be 66 participants (33 per group). This supports our goal of recruiting 88 participants (44 per condition) as yielding adequate power, based on retention of 75% of the enrolled participants. The current application proposes a change of grantee organization whereby the final 72 participants will be enrolled at KF. We will explore the possible influence of study site on the outcomes in *post-hoc* sensitivity analyses. We expect that the effects of study site are likely negligible given the constants of the study team and standardized manuals of operating procedures that guide all study aspects.

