Specific Aim 1. The primary analysis will involve a statistically efficient step-down testing approach using ANCOVA models to examine changes in CPS and thalamocortical RSFC (i.e., examining group differences in follow-up outcomes, adjusting for baseline). As the primary study outcome involves CPS based on SDMT scores, we will first perform an ANCOVA model on follow-up SDMT score, with group (exercise or control) as a between-subjects factor and baseline SDMT score as the covariate. If statistically significant (i.e., $p<.05$), we will then assess the effects of the intervention on thalamocortical RSFC. This second step will involve performing two separate ANCOVA models on follow-up RSFC between the thalamus and right MFG and ACC, respectively, with group (exercise or control) as a between-subjects factor and baseline RSFC between the thalamus and right MFG and ACC, respectively, as the covariates. We will require an alpha of .05 (corrected for multiple comparisons) for significance for thalamocortical RSFC outcomes. The correction for multiple comparisons will be achieved by establishing a suitable voxel cluster-level threshold through Monte Carlo simulations (using the 3dClustSim program, part of the AFNI suite of image analysis programs). Based on our pilot work¹², we expect significant group differences in SDMT score and RSFC between the thalamus and right MFG and ACC, respectively, at follow-up after controlling for baseline scores, whereby participants who are randomly assigned to the exercise group will demonstrate greater SDMT scores and stronger thalamocortical RSFC at follow-up compared with those who are randomly assigned to the control group.

Specific Aim 2. We will examine RSFC between thalamus/right MFG, and RSFC between thalamus/ACC, respectively, as two potential mediators of the effects of TMWX training on CPS, consistent with the methodologies of Baron and Kenny⁸⁹ and MacKinnon et al⁹⁰. This statistical mediation approach is consistent with the proposed gold standard approach for examining exercise-related mechanisms of cognitive

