improvement at the brain-systems level in the general population²⁸. As pre-conditions of the mediation analysis, we will first perform correlations among group (i.e., exercise or control), change in SDMT scores, and change in RSFC between the thalamus and right MFG and ACC, respectively, using Spearman's rho rank-order correlations (ρ)⁹¹ to test if those outcomes are interrelated. Consistent with our pilot work¹², we expect that TMWX training will be associated with improvements in CPS and increases in thalamocortical RSFC. Moreover, we expect that improvements in CPS will be associated with increases in thalamocortical RSFC. Then, to establish mediation, we will perform hierarchical linear regression models for evaluating each of the two mediators (i.e., changes in RSFC between thalamus/right MFG, and RSFC between thalamus/ACC, respectively), separately. This will involve regressing change in SDMT score on group in Step 1 and then adding change in the mediator in Step 2. In order to establish mediation, if the pre-conditions are met, group must influence change in SDMT in Step 1, and the mediator must influence change in SDMT score in Step 2 of the regression as well as attenuate the effect of group on SDMT scores (i.e., the effect of group on SDMT should be reduced and become non-significant between Step 1 and Step 2)⁸⁹. As such, we expect significant effects of group on change in CPS, and that the effect of group (i.e., exercise or control) on change in CPS will be attenuated, but not reach zero, when accounting for the effects of changes in thalamocortical RSFC. In other words, we expect that changes in thalamocortical RSFC will be partial mediators of the effects of TMWX training on CPS in persons with MS with impaired CPS.

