exploring and examining the impact of such losses, as we could have upwards of 25% drop-out, given that this sample includes persons with objective CPS impairment. Initially, analyses will be done on the data set using last observation carried forward and then on the actual data collected (case-wise deletion), followed by multiple imputation for missing data. All analyses at present are planned using SPSS software (version 25 or higher), although as new options continue to evolve with SAS or R; these will be considered if there are new tools for imputation that will help understand the impact of missing data. We believe that these imputations should involve fewer than 15% of the participants, which then should have minimal impact on the analyses. However, it is important to assess this from a best case and worst case scenario and if the results are consistent, then we can be more confident of our findings. If these analyses yield differing results – more exploratory analyses are required to understand if the differences in the outcomes are coming from the control condition or the intervention condition. If the control condition, the implications can be examined in one way and if the intervention condition, it is likely to add cautionary notes to the findings.

Interim and Final Analysis. We do not plan any interim efficacy or futility analyses. The study team will work together for publications on the protocol, fidelity monitoring plan, as well as the primary study outcomes.

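### The Aim 2 rule declares mediation only if the group effect loses significance, which often misses true partial mediation, and no test of the indirect effect is written out

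*Combined protocol and SAP*

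**What the plan says.** The rule stands in the SAP part of the combined document, under Specific Aim 2. Two connectivity changes (thalamus with right MFG, thalamus with ACC) are examined separately, "as two potential mediators of the effects of TMWX training on CPS, consistent with the methodologies of" two cited sources, references 89 and 90.

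Spearman correlations among group, SDMT change and RSFC change come first, as pre-conditions; no significance threshold is given for them. The models follow: "This will involve regressing change in SDMT score on group in Step 1 and then adding change in the mediator in Step 2".

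The decision rule opens "In order to establish mediation, if the pre-conditions are met, group must influence change in SDMT in Step 1". The mediator must also predict SDMT change in Step 2, and must weaken the group effect, which the SAP explains as: "the effect of group on SDMT should be reduced and become non-significant between Step 1 and Step 2". This last clause is attributed to reference 89.

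The section then predicts that the group effect "will be attenuated, but not reach zero, when accounting for the effects of changes in thalamocortical RSFC", and concludes: "we expect that changes in thalamocortical RSFC will be partial mediators of the effects of TMWX training on CPS".

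No estimate, test or confidence interval for the indirect effect appears there or elsewhere in the SAP. The protocol's own analysis section (5.3) contains no mediation analysis. What is taken from reference 90 is not stated.

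**The concern.** Whether RSFC carries part of the treatment effect is a question about the indirect effect: the effect of group on RSFC change (a) times the effect of RSFC change on SDMT change given group (b). In these regressions, a x b equals the drop in the group coefficient from Step 1 to Step 2. The plan therefore produces the right estimate but attaches no inference to it. It judges mediation partly by whether the remaining (direct) effect misses significance.

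That has two consequences. The clause is easier to satisfy when the direct effect is imprecisely estimated. And a mediator that carries a real share is rejected whenever the rest of the effect is still detectable, which is the situation that the SAP's own expectation of partial mediation makes likely.

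Hypothesis 2 belongs to a named specific aim, not an exploratory one. It could be reported as unsupported although RSFC carries a real share of the effect, with no interval to show how much mediation remains compatible with the data.

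**Working it through.** **The plan's own figure.** The SAP (Sample Size Considerations) sizes the trial for the Aim 1 ANCOVA only; there is no calculation for Aim 2.
- Inputs: partial eta-squared 0.11, alpha 0.05, power 0.80.
- f² = 0.11/0.89 = 0.1236, f = 0.352, and d = 2f = 0.703 for two equal arms.
- Noncentral F with noncentrality f² x N and df (1, N-3): power is 0.797 at N=65 and 0.803 at N=66.
- 66/(1 - 0.25) = 88, where power is 0.903.

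The stated 66 and 88 are reproduced.

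**Scale.** The 0.703 is adjusted for baseline, whereas Aim 2 analyses change scores. With equal variances and baseline/follow-up correlation r, the ANCOVA residual SD is σ√(1-r²) and the change-score SD is σ√(2(1-r)). So change-score d = 0.703 x √((1+r)/2). The documents do not give r. At an assumed r = 0.55, d = 0.703 x √0.775 = 0.62. The value 0.70 is reached only at r = 1 and is an upper bound.

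**Model (assumed).** RSFC change = a x group + N(0,1). SDMT change = (d - ab) x group + b x RSFC change + N(0, 1-b²). The total effect is d and the share mediated is ab/d. With a = 0.8 or 1.0 and b = 0.35 or 0.45, ab = 0.28, 0.35, 0.36 or 0.45. That is 45, 56, 58 or 73% of 0.62, and 40, 50, 51 or 64% of 0.703.

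**Rules compared.**
- Plan's full rule: three Spearman tests at p<.05 (threshold assumed), Step 1 group p<.05, Step 2 mediator p<.05, group coefficient reduced and p≥.05.
- The same rule without the last p≥.05 requirement.
- Proposed rule: Step 1 significant and indirect effect supported at 97.5%. Joint significance of a and b at .025 stands in for the bootstrap.

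The first two rules were run with 20,000 simulated trials per cell. N=66 is the planned number of completers; N=88 is everyone enrolled.

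| d | Share mediated | N | Full rule | Without the clause | Cost of clause (points) | Proposed rule |
|---|---|---|---|---|---|---|
| 0.62 | 45-73% | 66 | 33-54% | 50-63% | 9-17 | 45-64% |
| 0.62 | 45-73% | 88 | 42-66% | 69-78% | 12-28 | 66-81% |
| 0.70 | 40-64% | 66 | 33-59% | 57-74% | 15-25 | 51-74% |
| 0.70 | 40-64% | 88 | 37-67% | 78-87% | 21-41 | 74-89% |

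**Direction with precision.** At d = 0.70 with 50% mediated, the full rule succeeds in 45% of trials at N=66, 52% at 88, 49% at 132, 34% at 200 and 8% at 400. This trial stops at 88; the larger sizes only show that better data eventually make the rule fail.

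**Sensitivity to the share mediated.** A separate simulation (d = 0.703, b from 0.3 to 0.7, Pearson in place of Spearman) gives the full rule 2-18% at N=88 with 25% mediated and 69-78% with 75% mediated. Joint significance of a and b at .05 gives 22-63% and 82-100%.

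**Why Step 1 should stay.** If the interval alone decided, detection would look higher: 62-91% at N=66 and 81-98% at N=88. But at d = 0.70 and N=66, 10-17 of those points come from trials with no significant Step 1 effect. In the extreme case of zero total effect (a direct effect cancelling ab), that rule would declare mediation in 62-91% of trials at N=66, against about 2% under the plan.

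**The case against.** **The SAP contradicts itself.** A reader might infer this from the non-significance clause standing beside the forecast of partial mediation. The documents do not support it: a nonzero remaining effect can miss p<.05, so both statements can hold in one trial.

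**The rule always rejects partial mediation.** It does not. In the cells examined, between about a third and two thirds of true partial mediators pass. It is a tendency, and its strength depends on the unknown share mediated.

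**No indirect-effect test is intended.** This cannot be concluded. The SAP cites a second methodology, reference 90, whose content is not in the documents; the printed reference list ends at 70. What stands is narrower: the only decision rule written out is the one described above, and nothing says which source governs if the two disagree.

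**The sizes are assumed.** True: a, b, r and the share mediated are not in the documents. The direction does not depend on them. An added condition can only lower detection, and when a true direct effect remains, the loss grows with precision.

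**The indirect effect alone should decide.** Some would drop the Step 1 condition as well. That does not suit this plan. Hypothesis 2 (protocol section 2) is about explaining improvements caused by exercise. SAP Specific Aim 1 tests RSFC only after a significant SDMT result, and protocol 5.3 stops formal testing at the first non-rejection, although neither names Aim 2. Curing the defect does not require removing Step 1.

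**Conclusion.** The concern holds as a fault in the Aim 2 decision rule and should be fixed. The non-significance clause is a stated condition, it does not test the indirect effect, and it lowers the chance of recognising the partial mediation that the SAP expects. On the change-score scale, the loss is about 9-17 points at N=66 and 12-28 at N=88; at the upper bound d = 0.70 it is about 15-25 and 21-41. These figures assume r = 0.55 for the change-score scale, 40-73% mediated across the two scales, the paths listed in the working, and a .05 threshold for the Spearman pre-conditions.

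A reader might infer that the primary SDMT analysis or the sample size is in doubt. Neither is: both concern Aim 1, and the 66 and 88 reproduce.

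**What to change.** In SAP Specific Aim 2:
- Delete the requirement that the group effect become non-significant.
- Keep the condition that group must influence SDMT change in Step 1.
- For each mediator, declare mediation if Step 1 is significant and a percentile-bootstrap interval for a x b excludes zero, with 97.5% intervals or Holm across the two mediators.
- Report the direct effect, the proportion mediated and the Spearman correlations descriptively, not as gates.
- State what, if anything, is taken from reference 90.

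Optionally, repeat the test on the observed-case and multiply imputed data already planned under Treatment of Missing Data, because last observation carried forward sets both changes to zero for drop-outs. With 25% drop-out at N=88, b = 0 and no Step 1 condition, the 97.5% interval excluded zero in 5-9% of trials, against about 3% in 66 observed cases. Multiple imputation was not simulated.

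The cost is SAP wording and a bootstrap on regressions already planned; no new data are needed. The two-mediator adjustment takes some power: for example, 74% falls to 62% at N=66 with 40% mediated, before the Step 1 condition. The interval's false-positive rate per mediator at N=66 was 2.9-3.3% without Step 1 (nominal 2.5%), against about 1% for the current rule; adding Step 1 cannot raise it. Weak mediation stays hard to detect: at 30% mediated, the interval alone reaches 31-40% at N=66 and 42-57% at N=88. The direct effect and proportion mediated will be imprecise at this size.
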